### Table 1: Master Protocol RSSP Standard Schedule of Assessments

All P2P participants will be screened from PPMI and will have NSD characterization and staging applied prior to P2P screening.

Activity	Master Protocol Screening  Group A	Master Protocol Screening  Group B	Baseline/ Randomization within RSSP	Week 2	Mon 1	Mon 3	Mon 6	Mon 9	Mon 12	Mon 15	Mon 18	Mon 21	Mon 24 /Early Termination 	Initiation of Dopamin ergic Tx 	End of RSSP Treat ment	End of RSSP Treat ment Safety Call 
	<6 months from last PPMI*	≥6 months from last PPMI*														
	Clinic	Clinic	Clinic	Phone	Clinic	Clinic	Clinic	Tele1	Clinic	Tele1	Clinic	Tele1	Clinic	Clinic	Clinic	Phone
Window days Informed Consent	-90 to -1	-90 to -1	0	3 +	7 +	14 +	14 +	14 +	3 +							
Documentation of informed consent	Х	Х														
Screening Activities																
Inclusion /exclusion criteria	Х	Х	Х													
DAT eligibility	Х	Х														
General Activities																
Demographics 	PPMI	PPMI														
Family History 	PPMI	PPMI						4	Data uple	oaded pe	er PPMI E	DC				
Medical history 	PPMI	PPMI														
Socio-Economics 	PPMI	PPMI													1	
Physical Examination	Х	Х							Х				Х		Х	
Height and Weight 	Х	Х	Х		Х	Х	Х		Х		Х		Х	Х	Х	
Vital signs	Х	Х	Х		Х	Х	Х	Х	Х	Х	Х	Х	Х	Х	X	
Orthostatic BP	Х	Х	Х		Х	Х	Х	Х	Х	Х	Х	Х	Х	Х	Х	

Activity	Master Protocol Screening  Group A	Master Protocol Screening  Group B	Baseline/ Randomization within RSSP	Week 2	Mon 1	Mon 3	Mon 6	Mon 9	Mon 12	Mon 15	Mon 18	Mon 21	Mon 24 /Early Termination 	Initiation of Dopamin ergic Tx 	End of RSSP Treat ment	End of RSSP Treat ment Safety Call 
	<6 months from last PPMI*	≥6 months from last PPMI*														
	Clinic	Clinic	Clinic	Phone	Clinic	Clinic	Clinic	Tele1	Clinic	Tele1	Clinic	Tele1	Clinic	Clinic	Clinic	Phone
Window days	-90 to -1	-90 to -1	0	3 +	7 +	14 +	14 +	14 +	14 +	14+	14 +	14 +	14 +	14 +	14+	3 +
Neuro/Motor Assessments		1														
Participant Motor Function Questionnaire		Х				Х	Х	Х	Х	х	Х	Х	Х	Х	Х	
Freezing and Falls		Х							Х				Х		Х	
Neurological Exam	Х	Х							Х				Х		X	
MDS-UPDRS Part la	Х	Х			Х	Х	Х	Х	Х	Х	Х	Х	Х	Х	X	
MDS-UPDRS Part III Hoehn & Yahr	Х	Х	Х		Х	Х	Х		Х		Х		Х	Х	Х	

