MDS- UPDRS Part III /Hoehn & Yahr OFF/ON 						Post In	itiation c	f Dopam	inergic T	reatmen	t					
MDS- UPDRS Part IV 						Post In	itiation o	of Dopam	inergic T	reatmen	t					
MDS-UPDRS Part Ib and Part II	Х	Х			Х	Х	Х	Х	Х	Х	Х	Х	Х	Х	Х	
Modified Schwab & England ADL	Х	Х				Х	Х	Х	Х	х	Х	Х	Х	Х	Х	
Features of Parkinsonism		Х				Х	Х	Х	Х	Х	Х	Х	Х		X	
Other Clinical Features		Х				Х	Х	Х	Х	Х	Х	Х	Х		X	
Clinical Diagnosis	Х	Х				Х	Х	Х	Х	Х	Х	Х	Х	Х	Х	
Primary Research Diagnosis	Х	Х				Х	Х		Х		Х		Х	Х	Х	

Activity	Master Protocol Screening  Group A	Master Protocol Screening  Group B	Baseline/ Randomization within RSSP	Week 2	Mon 1	Mon 3	Mon 6	Mon 9	Mon 12	Mon 15	Mon 18	Mon 21	Mon 24 /Early Termination 	Initiation of Dopamin ergic Tx 	End of RSSP Treat ment	End of RSSP Treat ment Safety Call 
	<6 months from last PPMI*	≥6 months from last PPMI*														
	Clinic	Clinic	Clinic	Phone	Clinic	Clinic	Clinic	Tele1	Clinic	Tele1	Clinic	Tele1	Clinic	Clinic	Clinic	Phone
Window days	-90 to -1	-90 to -1	0	3 +	7 +	14 +	14 +	14 +	3 +							
Non-Motor Assessments																
Olfactory Testing (UPSIT)		Х							Х				Х		Х	
RBD Screening Questionnaire.		Х							Х				Х		Х	
Epworth Sleepiness Scale		Х							Х				Х		Х	
SCOPA-AUT		Х				Х			Х		Х		Х		Х	
Neuro QoL		Х							Х				Х		Х	
Cognitive and Psychiatric Assessments		1	1		1	1	1	1			I	1			1	
Montreal Cognitive Assessment	Х	Х							Х				Х		Х	
Clock Drawing		Х							Х				Х		Х	
Lexical Fluency		Х							Х				Х		Х	
Hopkins Verbal Learning Test- Revised		Х							Х				Х		Х	
Benton Judgment of Line Orientation		Х							Х				Х		х	
Modified Semantic Fluency (Animals only)		Х							Х				Х		х	
Letter Number Sequencing		Х							Х				Х		Х	

Activity	Master Protocol Screening  Group A	Master Protocol Screening  Group B	Baseline/ Randomization within RSSP	Week 2	Mon 1	Mon 3	Mon 6	Mon 9	Mon 12	Mon 15	Mon 18	Mon 21	Mon 24 /Early Termination 	Initiation of Dopamin ergic Tx 	End of RSSP Treat ment	End of RSSP Treat ment Safety Call 
	<6 months from last PPMI*	≥6 months from last PPMI*														
	Clinic	Clinic	Clinic	Phone	Clinic	Clinic	Clinic	Tele1	Clinic	Tele1	Clinic	Tele1	Clinic	Clinic	Clinic	Phone
Window days	-90 to -1	-90 to -1	0	3 +	7 +	14 +	14 +	14 +	3 +							
Symbol Digit Modalities Test		Х							Х				Х		Х	

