#### Footnote:

1. Tele (Video if possible) visits may be converted into in-person clinic visits as necessary at the discretion of the site investigator; vital signs and clinical safety labs will not be collected at Tele visits unless the visit is converted to an in-person clinic visit

2. Procedures, assessments, and samples collected as part of the main PPMI Clinical study (screening) may be used for this Master Protocol and will be uploaded into EDC by Data Management

- 3. Clinical Safety/Research Samples: See Section 12 and Appendix 3 for specific analytes. IgE should be collected at screening and as specified in each RSSP. HIV serology, HBV serology and Hep C antibody performed at screening only. Collect samples as outlined in the Laboratory Manuals; Collect Screening blood samples after other requisite tests for eligibility have been completed. For WOCBP, perform serum pregnancy test (HCG) at Screening; perform urine pregnancy test or (serum if required by the site) prior to injection of DaTscan and at all other indicated visits.
- 4. Skin biopsy and lumbar puncture tests will be repeated if last procedure/test performed  $\geq 12$  months of the P2P screening visit
- 5. Repeat DaTscan if last DaTscan was collected  $\geq$  3 months of the P2P screening visit.
- 6. The end of treatment is defined when last RSSP participant completes their month 24 visit for the assigned RSSP. All consented participants will remain active in the RSSP until the last subject completes the month 24 visit or until 24 months have passed since randomization (if terminated early). Following Month 24, participants will continue study visits every 3 months until the last participant randomized in the RSSP has had the opportunity to complete 24 months of follow-up on intervention. Participants will repeat the Months 15 24 visit schedules until the End of RSSP Treatment. Therefore, Month 27 will follow the same schedule of activities as Month 15; Month 30 will follow the same schedule of activities as Month 18; Month 33 will follow the same schedule of activities as Month 21; Month 36 will follow the same schedule of activities as Month 24 and so on (Table 4).

- 7. PPMI annual visit data may be used for P2P screening visits (group A or B)

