## 6.3 Key Exploratory Endpoints

- 1. The number of participants who progress from NSD stage 2B to NSD Stage 3 or higher
- 2. Clinical outcome as defined by the rate of progression in the MDS-UPDRS Total score from baseline through follow-up or the initiation of dopaminergic treatment and rate of progression in Part I & II subscores from baseline through follow-up.
- 3. Change in cognition as defined by the number of participants developing new syndromes of mild cognitive impairment (MCI) or dementia.
- 4. Change in functional status as measured by Penn Parkinson's Daily Activities Questionnaire-27 (PDAQ-27) from baseline through follow-up.
- 5. Time to progression milestones as defined by Brumm et  $al^1$ .

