#### Neuro/Motor Assessment:

- Participant motor function questionnaire (group B only)\*
- Freezing and Falls (group B only)\*

- Neurological Exam
- MDS-UPDRS Part Ia
- MDS-UPDRS Part III Hoehn & Yahr
- MDS-UPDRS Ib & Part II
- Modified Schwab & England ADL
- Assess Features of Parkinsonism (group B only)\*
- Other Clinical Features (group B only)\*
- Clinical Diagnosis
- Primary Research Diagnosis

Non-Motor Assessments:

- Administer Olfactory Testing: University of Pennsylvania Smell Identification Test (UPSIT: group B only)\*
- RBD Screening Questionnaire (group B only)\*
- Epworth Sleepiness Scale (group B only)\*
- SCOPA AUT (group B only)\*
- Neuro QoL (group B only)\*

Cognitive & Psychiatric Assessments:

- Montreal Cognitive Assessment
- Clock Drawing (for group B only)\*
- Lexical Fluency (group B only)\*
- Hopkins Verbal Learning Test-Revised (group B only)\*
- Benton Judgment of Line Orientation (group B only)\*
- Modified Semantic Fluency (Animals only) (group B only)\*
- Letter Number Sequencing (group B only)\*
- Symbol Digit Modalities Test (group B only)\*
- Trail Making Test (A and B) (group B only)\*
- Modified Boston Naming Test (group B only)\*
- Cognitive Change
- Cognitive Characterization
- State-Trait Anxiety Inventory for Adults (group B only)\*
- Geriatric Depression Scale
- QUIP (group B only)\*

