### 9.2 Baseline/Randomization Visit

The Baseline/Randomization Visit will take place in-person after the Master Protocol Screening Visit. The following procedures will be performed and are listed in the order to be completed:

- Confirm Master Protocol inclusion/exclusion eligibility
- Measure Weight
- Measure Vital signs and Orthostatic Blood Pressure
- Administer Neurological and Motor Assessments including: MDS-UPDRS Part III and Hoehn & Yahr.
- Perform Global Function Assessments including: CGI-S, PGI-S, Novel PRO, PDAQ-27
- Administer the C-SSRS Baseline questionnaire
- Collect research samples (urine and blood)

- Review and document concomitant medications
- Assess any accessible inclusion/ exclusion criteria for eligibility into all available RSSPs. This is done via available data obtained or collected in the Master Protocol Screening visit.
- Randomization to active study drug or placebo
- Assess and document AEs related to Master Protocol procedures
- Assess current medical conditions
- Assess pregnancy status

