#### 15.8.2 Change from Baseline in MDS-UPDRS Total and Part I & II Subscores

All three of these analyses will proceed in the same manner as the primary analysis specified for the MDS-UPDRS part III score, as specified in Section 15.1. The only difference will be that the outcome is modified accordingly.

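### MDS-UPDRS Parts I and II are not scheduled at the Baseline visit, so the Part I, Part II and Total slopes start from a screening or older PPMI score, which can modestly dilute the estimated slowing

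*Protocol*

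**What the plan says.** **Schedule.** The only MDS-UPDRS instruction for the Baseline visit in Section 9.2 is "Administer Neurological and Motor Assessments including: MDS-UPDRS Part III and Hoehn & Yahr". Table 1 matches it. The row "MDS-UPDRS Part III Hoehn & Yahr" is marked at both screening columns, at Baseline, and at the in-clinic visits from Month 1. The row printed as "MDS-UPDRS Part la" (Part Ia) and the row "MDS-UPDRS Part Ib and Part II" are marked at both screening columns and again from Month 1, with the Baseline cell empty. Section 9.1 lists Part Ia and "MDS-UPDRS Ib & Part II" at screening without restricting them to Group B, so both groups have them there.

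**Endpoint.** Item 2 of Section 6.3 covers progression in the Total score from baseline and "rate of progression in Part I & II subscores from baseline through follow-up". Section 15.8.2 states: "All three of these analyses will proceed in the same manner as the primary analysis specified for the MDS-UPDRS part III score". The Section 15.1 model estimates a difference in rate of change from baseline to the last visit. The synopsis places the key exploratory endpoints in the final RSSP reports.

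**Age of the earlier score.** Section 9.1 allows screening up to 90 days before Baseline. Footnote 7 of Table 1 adds: "PPMI annual visit data may be used for P2P screening visits (group A or B"). Reused scans and samples have age limits (DaTscan and lumbar puncture/skin biopsy in footnotes 5 and 4, MRI in Section 13.2). None is stated for MDS-UPDRS.

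**The concern.** Part III has a score at randomisation. Parts I and II do not, so neither does a Total whose components share one date. A Total at baseline must either add Part III from the Baseline visit to Parts I and II from another day, or fall back on the screening Total.

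The stretch between the early score and randomisation is untreated in both arms. If that stretch enters the slope, part of the fitted time axis carries no treatment effect, and the estimated slowing can shrink. The length of the stretch also varies between participants. Part I, Part II and Total would then not be on the same footing as the Part III analysis they are meant to mirror. A score not taken before the first dose cannot be recovered later.

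**Working it through.** The protocol gives no effect size, power or sample size for Part I, Part II or Total, so there is no stated figure to reproduce. The check below concerns the direction and size of any dilution.

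**Inputs**
- Visits after the first score (Table 1): Parts I/II at Months 1, 3, 6, 9, 12, 15, 18, 21, 24. Total at Months 1, 3, 6, 12, 18, 24, because Part III is not done at the tele visits.
- Lag L of the first score before Baseline: up to 90 days (about 3 months) on the scheduled path. With footnote 7, a Group A visit just under 6 months before screening plus the 90-day window gives about 9 months. The 12-month case is an assumption.
- True slowing of 30%, borrowed from the Section 15.3 scenarios for the primary endpoints (assumption).
- Placebo slope 1. Active slope 1 before randomisation and 0.70 after (assumption).

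**Formula, score at its true date.** The arm difference is proportional to d = max(t, 0). With balanced data and separate intercepts, the fitted slope difference divided by the true one is

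R = Σ(t − t̄)d / Σ(t − t̄)²

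The placebo slope is still 1, so the slowing read off is 30% × R.

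- Parts I/II, L = 3: n = 10, Σt = 106, Σt² = 1846, Σd = 109, Σtd = 1837. Denominator 1846 − 106²/10 = 722.4; numerator 1837 − 106 × 109/10 = 681.6. R = 0.944, slowing 28.3%.
- Total, L = 3: n = 7, Σt = 61, Σt² = 1099, Σd = 64, Σtd = 1090. Denominator 1099 − 61²/7 = 567.4; numerator 1090 − 61 × 64/7 = 532.3. R = 0.938, slowing 28.1%.

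**Same score coded as time 0.** The arm difference is then exactly proportional to coded time, so the slope difference is 100% of true. Only the placebo slope is inflated, because the first placebo value is 3 units low.

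- Parts I/II: 1 + 3 × 10.9/648.9 = 1.050, so slowing = 30%/1.050 = 28.6%.
- Total: 1 + 3 × 9.143/504.9 = 1.054, so slowing = 30%/1.054 = 28.5%.

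**Results (slope difference as % of true; slowing read off)**

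| First score | Coding | Parts I/II | Total |
|---|---|---|---|
| At Baseline | – | 100%; 30.0% | 100%; 30.0% |
| 1.5 months early | true date | 97.3%; 29.2% | 97.1%; 29.1% |
| 3 months early | true date | 94.4%; 28.3% | 93.8%; 28.1% |
| 3 months early | time 0 | 100%; 28.6% | 100%; 28.5% |
| 9 months early | true date | 81.4%; 24.4% | 79.5%; 23.8% |
| 9 months early | time 0 | 100%; 26.1% | 100%; 25.8% |
| 12 months early | true date | 75.0%; 22.5% | 72.5%; 21.7% |
| 12 months early | time 0 | 100%; 25.0% | 100%; 24.6% |

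A common-intercept fit (assumed variance components) at 3 months, true date, gives 93.0% for Parts I/II and 92.4% for Total. With visits to Month 48, the 3-month loss for Parts I/II falls to under 2% (98.2%; slowing 29.5%). Using only Month 1 onward returns 30.0%.

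**The case against.** The strongest reply is that the protocol often lets a screening or PPMI value serve as baseline. DAT SPECT, itself a primary endpoint, has no Baseline-visit measurement; neither do SCOPA-AUT, Neuro-QoL or MoCA. This stands. A reader might infer that the gap is peculiar to Parts I and II, or that participants have no usable pre-treatment score, and the documents support neither. What remains is narrower. Part III, PDAQ-27, CGI-S and PGI-S are taken at Baseline, and Section 15.8.2 ties Part I, Part II and Total to Part III.

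Second, which value is the baseline and how its time is coded may well be settled in the SAP, and a model with the slope change placed at randomisation would remove the dilution. That also stands. But a SAP can only choose among scores that exist; it cannot supply one that the schedule omits. Section 9 lets an RSSP add procedures, but an addition in some regimens only would leave the shared placebo group with mixed starting points.

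Third, the large losses rest on an option. Parts I and II are scheduled at P2P screening for both groups, and footnote 7 is permissive. The documents do not say how often PPMI scores will be substituted, so the 9- and 12-month rows cannot be read as the typical case.

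**Conclusion.** The mismatch between endpoint and schedule is real, and two places in the protocol agree on it. Its effect is modest. On the scheduled path, at the 90-day limit and with 24 months of follow-up, a true 30% slowing reads as about 28 to 28.6%. The tested slope difference is about 92 to 94% of true if the early score is dated truly within one straight line, and 100% if it is coded as time 0. Losses near 20% or more need PPMI scores about 9 months old or older, dated as such.

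A reader might conclude that any slowing is necessarily understated. That goes too far: under time-0 coding the tested difference is unbiased and only the percentage shrinks, and the protocol does not fix the coding. There is no bias under the null, provided the lag has the same distribution in both arms, as randomisation ensures for concurrent controls. The primary endpoints are unaffected, as are the stated sample size, power and type I error. A reader might also think that eligibility is at stake. However, staging is applied before P2P screening, and adding Parts I and II at Baseline would still leave MoCA unrepeated, so it would not supply current Stage 2B anchors.

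The sizes rest on the assumed linear trajectories, the borrowed 30% effect, an effect that starts at randomisation, and complete visits. Longer follow-up shrinks the loss; shorter follow-up enlarges it.

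**What to change.** Add MDS-UPDRS Parts Ia, Ib and II to the Baseline/Randomization column of Table 1 and to the list in Section 9.2, completed before the first dose. In Section 15.8.2, state that the Baseline-visit scores are the time-zero values for Part I, Part II and Total, and that the screening score is used only if the Baseline score is missing.

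With a Baseline score, the check above returns 100% of the slope difference and 30.0% slowing. The cost is protocol and schedule wording, plus a few more minutes of assessment at an in-person visit where Part III is already done. No new visit is needed, and no sample size, power or alpha figure changes.

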## 9.3 Week 2 Telephone Visit

This visit will take place  $14 \pm 3$  days after the Baseline Visit via telephone. The following procedures will be performed per the PPMI Assessment Manual and documented and are listed below:

- Digital Assessment per the PPMI Digital Sub Study (as needed)
- Administer C-SSRS Since Last Visit Short Form
- Concomitant medication review
- LEDD medication initiation log (as needed)
- Assess and document AEs
- Assess current medical conditions
- Assess pregnancy status (as needed)
- Surgery for PD (as needed)

## 9.4 Month 1 Visit

This visit will take place in person approximately  $28 \pm 7$  days after the Baseline Visit. The following procedures will be performed:

- Measure Weight, Vital Signs & Orthostatic Blood Pressure
- Administer MDS-UPDRS Part I-III
- Digital Assessment per the PPMI Digital Sub Study (as needed)
- Collect blood samples for clinical safety labs
- Perform 12-lead electrocardiogram
- Administer C-SSRS Since Last Visit Short Form
- Concomitant medication review
- LEDD Medication Initiation Log (as needed)
- Assess and document AEs
- Current Medical Conditions Review
- Report of pregnancy (as needed)
- Surgery for PD (as needed)

## 9.5 Treatment Visits

Treatment visits will be conducted every 3 months (up to 24 months)  $\pm$  14 days after the Baseline Visit. Visits will be performed in person at the study clinic at months 3, 6, 12, 18, 24 and every 3 months after month 24 until the participant has completed the RSSP, or as necessary per the RSSP. Tele visits (audio/visual if possible) will be performed at visits 9, 15, and 21 unless in person visits are necessary at the discretion of the site investigator. Televisits will follow the same schedule of activities as outlined below with the exclusion of the assessments that cannot be completed remotely (see Schedule of Activities for details).

#### Month 3 Visit

- Measure Vital Signs & Orthostatic Blood Pressure, Weight
- Administer Neuro/Motor Assessments per the SOA (Table 1)
- Administer SCOPA-AUT
- Administer Cognitive and Psychiatric Assessments: Cognitive Change and Cognitive Characterization
- Perform Global Function Assessments: including CGI-S, PGI-S, PDAQ-27, Novel Participant Reported Outcomes
- Digital Assessment per the PPMI Digital Sub Study (as needed)
- Collect blood samples for clinical safety labs
- Administer C-SSRS Since Last Visit Short Form
- Concomitant medication review
- LEDD Medication Initiation Log (as needed)
- Assess and document AEs
- Current medical conditions review
- Report of Pregnancy (as needed)
- Surgery for PD (as needed)

#### Month 6 Visit

- Measure Vital Signs & Orthostatic Blood Pressure, Weight
- Administer Neuro/Motor Assessments per the SOA (Table 1)
- Administer Cognitive and Psychiatric Assessments: Cognitive Change, Cognitive Characterization, State Trait Anxiety Inventory for Adults, Geriatric Depression Scale, QUIP
- Perform Global Function Assessments: PDAQ-27
- Digital Assessment per the PPMI Digital Sub Study (as needed)
- Collect blood samples for clinical safety labs
- Administer C-SSRS Since Last Visit Short Form
- Collect research samples (blood and urine)
- Concomitant medication review

- LEDD medication initiation log (as needed)
- Assess and document AEs
- Current medical conditions review
- Report of Pregnancy (as needed)
- Surgery for PD (as needed)

#### Month 9 Visit

At month 9, a tele (audio/visual) visit will be performed, the following assessment will occur:

- Administer Neuro/Motor Assessments per the SOA (Table 1)
- Administer Cognitive and Psychiatric Assessments: Cognitive Change and Cognitive Characterization
- Digital Assessment per the PPMI Digital Sub Study (as needed)
- Administer C-SSRS Since Last Visit Short Form
- Concomitant medication review
- LEDD medication initiation log (as needed)
- Assess and document AEs
- Current medical conditions review
- Report of Pregnancy (as needed)
- Surgery for PD (as needed)

Please note, this visit can be converted to an in-person visit if needed, where the following would be collected in addition to the above:

- Measure Vital Signs & Orthostatic Blood Pressure, and Weight.
- Collect blood samples for clinical safety labs

#### Month 12 Visit

- Perform physical examination
- Measure Vital Signs & Orthostatic Blood Pressure, Weight
- Administer Neuro/and Motor Assessments per the SOA (Table 1)
- Administer Non-Motor Assessments: Olfactory testing UPSIT, RBD Screening Questionnaire, Epworth Sleepiness Scale, SCOPA- AUT, Neuro QoL
- Administer Cognitive & Psychiatric Assessments per the SOA (Table 1)
- Perform Global Function Assessments: including CGI-S, PGI-S, PDAQ-27, Novel Participant Reported Outcomes
- Digital Assessment per the PPMI Digital Sub Study (as needed)
- Collect blood samples for clinical safety labs
- Perform 12-lead electrocardiogram
- Administer C-SSRS Since Last Visit Short Form
- Collect research samples (blood and urine)

- LP
- Dopamine Transporter Injection & SPECT Imaging (with pregnancy test prior to DAT)
- MRI
- Concomitant medication review
- LEDD medication initiation log (as needed)
- Assess and document AEs
- Current medical conditions review
- Report of Pregnancy (as needed)
- Surgery for PD (as needed)
- Visit status

